#### **4. Study Design**

We will conduct a two-arm randomized controlled trial to examine the feasibility, acceptability, and likely effect of an unconditional cash transfer intervention on self-reported and objectively measured health behaviors and outcomes among low-income adults. A detailed outline of study design can be found in Study Procedures.

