##### **4.2. Target Population**

The study population will be comprised of primary care patients at Penn Family Care in West Philadelphia. We will enroll a total of 100 participants — 50 will be assigned to the usual care arm (Arm 1) and 50 will be in the intervention arm (Arm 2).

Participants enrolled by Penn Researchers: 100

Participants enrolled by Collaborating Researchers: 0

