Study staff will not have any involvement in the clinical care of potential participants. Recruitment will be done using a batched approach starting with 1) MyPennMedicine messages, followed by 2) Text messages, and finally 3) QR Codes in the clinic. Potentially eligible patients will first be contacted using a MyPennMedicine message with a REDCap survey link to our study interest form. For participants who respond to the survey interest form, the variables phone, patient name, DOB, and last visit date will be added to our REDCap project. Participants that do not complete an interest form via MyPennMedicine will be sent a text asking if they'd like to complete the online interest form via text, or if they would like to receive a call by research study staff with additional information about the study. Research staff will follow-up with a phone call for those who did not complete the interest form via text and ask if they'd like to complete the interest form over the phone. Research staff will be able to confirm the participant's identity over the phone by using name and DOB. Survey interest forms will be matched with the eligible EHR list pulled from SlicerDicer to confirm eligibility. Eligible participants will be contacted by phone to confirm interest in the study and schedule the baseline appointment. Study staff will describe the intervention and inform potential participants that the cash transfers may lead to SSI slightly overpaying them and asking for money back, which they can ask SSA to waive. Participants will also be informed that our team has received a notice from the state of Pennsylvania that the study payments will not count as income for state programs such as SNAP, TANF, and Medicaid, so their eligibility for these programs **will not** be affected by their participation. Eligible and interested potential participants will then be scheduled for an in-person baseline visit with study staff, where informed

consent will be obtained (see consent procedures, below, for additional details). The in-person visits will take place at [name] at the Psychology of Eating and Consumer Health Lab at the University of Pennsylvania (PI: [name]).

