Written consent will be obtained from participants during the initial in-person visit, prior to the study session. A single consent will be used for all study activities except the qualitative interviews, which will involve a separate consent process. The following data will be collected during the baseline assessment:

- Survey data – Study staff will administer an in-person REDCap survey that will capture the following:
  - Sociodemographics including age, sex, gender, address of residence, zipcode, race, ethnicity, sexual orientation, marital status, schooling attainment
  - Economic data including work, income sources (including government programs such as SNAP, TANF, and WIC), and total household income
  - Food security assessment in accordance with USDA methodology
  - Utility security (Home Energy Insecurity Scale)
  - Housing data including living situation, household composition, and housing security
  - Health-Related Quality of Life (CDC HRQOL-4)
  - Health Spending
  - Tobacco use (CDS-5)
  - Alcohol use (AUDIT-C)
  - Medication Adherence (ARMS)
  - Kessler Psychological Distress Scale (K6+)
  - CFPB Financial Stress Scale
  - Perceived Stress Scale (short form)
  - State Trait Anxiety Inventory (State questions only)
  - Time preference measures
  - Acceptability of Intervention Measure (follow up only)
- Electronic Medical Record
  - Number of ED/Hospital visits in last 3 months
  - Number of non-ED visits in last 3 months
  - Number of chronic medications
  - Chronic medical conditions (problem list)
- Objective data (measured by study staff and entered directly into REDCap)
  - Height
  - Weight
  - Blood pressure
- Cognitive testing (mental bandwidth)
  - Psychomotor Vigilance Task (PVT)
    - PVT is a computer-based task that assesses attentional vigilance, asking participants to press a button when a stimulus appears on a screen and measuring reaction time and accuracy
    - For this computer-based task, no identifying information is entered, and immediately upon completion the program puts out the relevant data (e.g. reaction time, accuracy), which will be directly and immediately entered into REDCap by study staff
- W9 and C2

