  - W9 (including SSN) and C2 will be collected for all participants . These will be completed by paper and stored in a secure location only accessible by study

personnel. At the end of the study, W9 forms will be scanned and sent via SecureShare to [name] to be logged into the Greenphire W-9 Database. Once scanned, paper copies will be shredded.

At the end of the baseline assessment, participants will be randomized using a permuted block technique with block size of 4 to either usual care (Arm 1) or to the unconditional cash transfer intervention (Arm 2). Participants in Arm 2 will receive an unconditional cash transfer of \$125 every 2 weeks for 8 payments via ClinCard, for a total of \$1000. In addition, 16 participants will also be randomly selected to receive a blood pressure cuff to take home. Of these 16, 8 will be blood pressure cuffs that wirelessly transmit readings to an app on their mobile phone. Participants that receive a blood pressure cuff will be asked to take a blood pressure reading weekly for the duration of their enrollment period, and record their reading via a REDCap survey link sent by text. Those receiving a wireless blood pressure cuff will transmit their readings wirelessly, as well as record their reading in the weekly REDCap survey link. The goal of this procedure is to pilot test the feasibility of this technology and approach for a future, larger study.

All participants will be asked to return for an in-person assessment at month 3. This assessment will include all elements of the baseline assessment. Additionally, intervention participants will complete the Acceptability of Intervention Measure and be asked a survey question about how the cash transfer was used. Participants randomized to receive a blood pressure cuff will also be asked to complete a short survey regarding their acceptability and use of a blood pressure cuff at home.

Via ClinCard, all participants will receive \$25 compensation for completing the baseline assessment, and \$50 for completing the follow-up assessment. Participants providing at-home blood pressure readings will receive an additional \$3 per reading (maximum \$3 per week, \$48 total).

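### A single fixed block size of 4, with no concealment described, makes an expected one third of allocations determinable by anyone who knows the block size and all earlier allocations

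*Protocol*

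**What the plan says.** - **Method.** Protocol section 5.1 says participants will be "randomized using a permuted block technique with block size of 4". No other size and no stratification factor is mentioned.
- **Size and site.** Section 4.2 plans 50 per arm and records "Participants enrolled by Collaborating Researchers: 0". Section 5.1 places the study visits in one laboratory.
- **Timing.** "At the end of the baseline assessment, participants will be randomized", so allocation follows consent and the baseline measures at the same visit.
- **Who does what before allocation.** Section 5.1 says "Eligible participants will be contacted by phone to confirm interest in the study and schedule the baseline appointment". At the visit, "Study staff will administer an in-person REDCap survey" and also take the blood pressure, height and weight readings. Section 5.2 has study staff go through the consent form. No division of these roles is stated.
- **What is not said.** The available text does not state who generates or holds the sequence, how the next allocation is hidden, whether staff are kept from the block size, or who is blinded. The nearest text is the SAP rule (Data Analysis) that data exclusions are settled before arm is linked back. That covers data cleaning, not recruitment or assessment.

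**The concern.** Randomising after consent and baseline protects a trial only if the next allocation cannot be foreseen. In a fixed block of 4 at 1:1, the last place is always settled by the first three, and the third is settled whenever the first two match. The person running the next baseline visit may have closed the preceding ones, and may therefore know their allocations.

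Two things are at stake. One is who gets consented when a given arm is expected. The other is the baseline scores themselves. The staff-administered survey covers food security, utility security, the CFPB financial scale, perceived stress, state anxiety and the ARMS adherence scale. All six supply SAP primary outcomes. The primary test is the arm-by-time interaction, so a baseline score coloured by an expected allocation goes straight into the treatment contrast. Section 2 of the Protocol wants this pilot to supply effect sizes for a larger trial, so a distorted contrast would be carried forward.

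**Working it through.** The documents give no predictability figure, so there is none to reproduce. As a consistency check, 100 / 4 = 25 complete blocks and 25 x 2 = 50 per arm, which agrees with Protocol section 4.2.

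**Inputs:** block size 4 (section 5.1); two arms, 50 each (section 4.2); recruitment March to July 2023 (section 4.1).

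**1. Certain allocations.** There are 4!/(2!2!) = 6 equally likely orders of AABB. An allocation is certain when one arm's two places are already used.

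| Place in block | P(certain) | P(best guess correct) |
|---|---|---|
| 1 | 0 | 1/2 |
| 2 | 0 | 2/3 |
| 3 | 1/3 | 1/3 x 1 + 2/3 x 1/2 = 2/3 |
| 4 | 1 | 1 |

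- Certain share: (0 + 0 + 1/3 + 1)/4 = 33.3%.
- Best-guess accuracy: (0.500 + 0.667 + 0.667 + 1)/4 = 70.8%, against 50% under simple randomisation.

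**2. Count in 100 participants.** Each block has one certain place, or two with probability 1/3. The total is 25 + Binomial(25, 1/3).

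- Mean: 25 + 8.3 = 33.3.
- SD: sqrt(25 x 1/3 x 2/3) = 2.4.
- Possible range: 25 to 50, with a 98% chance of 28 to 38.

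**3. Prediction at booking.** Suppose one randomisation is still pending when the person is booked. Only place 4 can then be certain, and only if the first two allocations match: (1/3)/4 = 1/12 = 8.3%. With two or more pending the share is 0%. March to July is about 22 weeks, so 100/22 gives about 4.5 randomisations a week. Several booked visits would usually be pending.

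**4. Passage into the estimate.** For a linear outcome with complete data, the interaction is (intervention month 3 minus baseline) minus (control month 3 minus baseline). Suppose the baseline scores of only the certain cash-arm participants are shifted by d (an assumed amount). By symmetry they are one third of that arm in expectation, so the estimate moves by d/3 in the opposite direction. Logistic models for the categorical food and utility outcomes have no exact equivalent, but their baseline values also enter the interaction.

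**5. Varying the block sizes.** Simulation of 2,000 lists of 100, with an observer who knows the set of sizes and all earlier allocations:

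| Sizes | Certain | Best guess correct |
|---|---|---|
| 4 | 33.3% | 70.9% (exact 70.8%) |
| 4, 6 | 5.5% | 69.2% |
| 4, 6, 8 | 2.3% | 67.8% |

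If bias from guessing scales with 2p - 1, it falls from 2 x 0.708 - 1 = 0.417 to 2 x 0.678 - 1 = 0.356, about 15% lower. The largest imbalance at participant 100 is 4 (52 against 48), when a block of 8 stops half way with all four places in one arm.

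**The case against.** A reader might infer that staff in this trial know a third of allocations beforehand. The documents do not support that. It would require the same people to know the block size and see every earlier allocation in order, and neither is stated. Nor is the block size shown to have been public during recruitment. The term open-label does not appear either; visibility of arm is inferred from cash versus usual care and from the arm-specific questions at month 3. The text read for this review also lacks a few pages of each document, so missing concealment text is judged on what was available.

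A reader might also picture needier patients being booked into known cash slots. This is weak. Prediction at booking is 8.3% or nil unless staff reorder visits. Income, food security and utility security are recorded at the baseline visit, after booking, and every participant is on Medicaid.

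Some outcomes are little exposed. Psychomotor vigilance results are produced by computer, visit counts come from the EHR, and blood pressure is exploratory in the SAP. The scales are mostly established instruments answered by the participant, and no motive for distortion is shown.

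The plan also has partial safeguards. Stable differences between arms largely cancel in a comparison of change, and covariates that differ at baseline trigger an adjusted re-analysis. Neither closes the gap. People chosen while in temporary hardship would tend to improve anyway, which would look like benefit. The SAP's covariate list does not include the baseline outcome scales, and covariate adjustment would not repair a baseline score recorded with an allocation in mind.

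The limits on knowledge, booking and exposed outcomes stand. The predictability of the stated scheme also stands.

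**Conclusion.** The point holds as a weakness of the stated scheme, not as evidence of bias. An expected 33 of 100 allocations are certain, and 70.8% can be guessed correctly, for an observer who knows the block size of 4 and all earlier allocations. Those two conditions are assumptions. They are plausible because allocation closes a visit run by study staff and no separation of roles is described. The one third is an expectation, and it applies to consent and baseline assessment of the next person to be randomised, not to booking. The size of any resulting bias cannot be worked out from the documents; d/3 shows only how it would pass through. This is a cheap improvement.

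**What to change.** In Protocol section 5.1, replace the fixed size with text on these lines: allocation 1:1 in permuted blocks of randomly varying size; sizes not disclosed to staff who recruit, consent or assess; list generated and held by someone outside recruitment; each allocation released only after that participant's baseline form is locked. Sizes of 4, 6 and 8 would serve, but should be recorded in a restricted document rather than in the protocol. State also who is blinded.

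The parts belong together. Varying the sizes removes nearly all certainty (about 2-3% of allocations remain certain), but lowers best-guess accuracy by only about three points. Withholding the sizes and locking the baseline form before release must therefore carry much of the protection.

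The cost is a short amendment, a regenerated list, a list holder outside recruitment, and set-up of form locking and controlled release. The arms may differ by up to about 4 participants instead of being exactly 50/50, which is of little consequence for these comparisons.

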## **5.2. Consent**

Randomized-controlled trial consent: Consent will be obtained from participants during the initial in-person visit, prior to the study session. A single consent will be used for all study activities except the qualitative interviews, which will involve a separate consent process. Assent will be confirmed prior to the follow up session. Participants will be provided a copy of the consent form, which will then be reviewed with the participant by study staff, and will only proceed with the study if they agree to consent. The consent form will be in English and will clearly state the purpose, eligibility criteria, study procedures, potential risks and benefits of participation, and the subject's right to refuse to participate or withdraw from the study. In particular, potential participants will be informed about the small impact on SSI benefits. We will provide information in the informed consent and welcome packet explaining that study payments are not considered countable income for the following list of government assistance programs, as well as information about how to report the income to ensure it does not affect eligibility:

- Temporary Assistance for Needy Families (TANF),
- Modified Adjusted Gross Income (MAGI) Medical Assistance (MA)
- non-MAGI MA including Home and Community-Based Services categories,
- Supplemental Nutrition Assistance Program (SNAP),
- Low-Income Household Water Assistance Program (LIHWAP),
- Low-Income Home Energy Assistance Program (LIHEAP).

It will be emphasized that participation in the study will not affect the right to care or services to which the potential participant would otherwise be entitled. It will be emphasized that only a subset of participants will be interviewed. Written consent will then be obtained and documented in REDCap.

Qualitative interview consent: Prior to conducting the interview, the interviewer will speak with participants on the phone and explain to participants that their participation is voluntary (see attached verbal consent script). The interviewer will also go over confidentiality and privacy with the participants. Participants will be informed that they can discontinue their participation at any time. The interviewer will answer any questions the participant has. Should the participant choose to participate in the study, the interviewer will document that they obtained verbal consent in REDCap.

## **6. Subject Compensation**

All subject compensation will be through ClinCard.

All participants will receive \$25 compensation for completing the baseline assessment, \$50 for completing the follow-up assessment. Participants providing at-home blood pressure readings will also receive \$3 per reading (maximum \$3 per week, \$48 total). Participants completing the in-depth interview will receive an additional \$35.

Participants in the intervention arm will also receive \$125 after completion of the baseline assessment, and an additional \$125 every 2 weeks for 8 total payments (\$1000 total).

## 7. Analysis Plan

AIMS 1 & 2: Data will be descriptively summarized and evaluated for quality prior to analysis. Means and standard deviations will be used to characterize continuous variables such as weight and blood pressure, and frequencies and percentages will be used to describe categorical variables. Medians and interquartile ranges will be reported for continuous variables that exhibit skewness. Data will be descriptively summarized overall and by condition.

All outcomes will be analyzed at the participant level. Analyses will employ population-averaged marginal models estimated by Generalized Estimating Equations (GEE) to account for correlations among the within-person baseline and follow-up measurements. Marginal models estimated by GEE are advantageous for their population-level interpretation and robustness of estimated effects to the assumed correlation structure among repeated measurements (meaning unbiased estimates of the effect of the behavioral intervention will be obtained whether or not the correlation among repeated measurements within a participant is modeled correctly). Clusters will be defined at the level of the participant for all analyses, and independence working correlation will be assumed. Linear models will be used for continuous outcomes and logistic models for categorical or ordinal outcomes.

Models will include intervention, measurement timepoint, and the interaction of intervention and measurement timepoint as categorical variables. The primary analysis testing the effectiveness of the cash transfers compared to the control arm will be evaluated by the test of the null hypothesis that the intervention-measurement timepoint interaction coefficient is 0, denoting no difference in the change in respective outcomes from baseline to month 3 between intervention and control. We will evaluate the sensitivity of estimated intervention effects to imbalances in baseline covariates and missing data. To assess the impact of imbalance in baseline covariates, outcomes will be reanalyzed in models that adjust for baseline covariates that differ significantly at the 0.05 level by condition. We will evaluate sensitivity to missing data by inverse probability of weighted GEE and multiple imputation. The Holm procedure at a family-wise error rate of 0.05 will be used to account for multiple comparisons in testing differences in 9 primary outcomes between the two groups (number of ED visits, number of non-ED visits, medication adherence, smoking, alcohol use, food security, utility security, health expenditures, and financial stress).

Aim 3 – Qualitative interviews: Qualitative analyses will be guided by an integrated approach that includes identification of a priori attributes of interest and identification of emergent codes and themes. A comprehensive coding scheme will be developed and applied to all data to produce a fine-grained descriptive analysis. All transcribed interview data will be imported into Nvivo for thematic coding. A single analyst will review and code all transcripts. The analysis will yield an understanding of any unanticipated or anticipated consequences of the study and cash transfer provision while also elucidating pathways through which cash transfers influence health behavior.

## **9. Human Research Protection**

The team includes investigators experienced in clinical medicine, health behavior interventions, economic interventions, clinical trials, behavioral economics, and program evaluation.

### **9.1 Data Confidentiality**

- Paper-based records will be kept in a secure location and only accessible to personnel involved in the study
- Computer-based files will only be made available to personnel involved in the study through the use of access privileges and passwords
- Only 4 members of the research team will have access to the dataset exported from the EPIC report created through SlicerDicer, which contains MRN
  - [name], Analyst
  - [name], PI
  - [name], PI
  - [name], PM
- Wherever feasible, identifiers will be removed from study-related information
- Audio and/or video recordings will be transcribed and then destroyed to eliminate audible identification of subjects

### **9.2 Subject Confidentiality**

[name] is a UPHS physician with access to SlicerDicer who has completed SlicerDicer research training through Penn Knowledge Link. He will be generating the eligibility dataset on SlicerDicer and exporting the data to an EPIC Report using the IRB-approved protocol number. He will send recruitment MyPennMedicine messages directly through EPIC to potential participants on this report. He will also download this dataset as a .csv file onto a UPHS Computer, and this dataset will be uploaded onto REDCap for the team to use during follow-up of people completing the interest form, to assess for eligibility.

Data will be entered directly on encrypted University of Pennsylvania computers into the web-based password-protected REDCap database. Collected Protected Health Information (PHI) will include the following: Name, address (for the purpose of ClinCard compensation), zip code, telephone number, and social security number (for the purpose of ClinCard compensation). Participants will automatically be assigned a study ID through the REDCap system. When records are complete, data will be downloaded from the web-based system with the generated study ID. Protected Health Information (PHI) will be delinked from the data and inaccessible to all study staff aside from the Investigators. At the end of the study, a list of MRNs for consented study participants will be submitted in a DACS request to obtain their active problem list, medications history, and visits (office, ED, hospital) 3 months before and after their study start date. This limited dataset will be used for analysis and will be maintained on an encrypted and password-protected University of Pennsylvania server accessible only to the Investigators.

**Qualitative interviews:** Audio recordings of interviews will be uploaded securely for transcription after sessions have been completed. Transcripts will be identifiable only through the participant identification number assigned for the purposes of the research. Only the study team will have access to these transcripts. Once all analysis and write up is complete, the interview transcripts will be destroyed. The data will not be distributed for future research studies. Transcriptions will be linked to the remainder of the study data through the study ID, and any identifying information inadvertently collected during recording will be immediately deleted from the transcripts. Transcripts will be stored in an electronic NVivo database on fire-walled servers accessible only to authorized project personnel.

Patient identifiers will be destroyed.

